### 5.3.2.10. Effectiveness non-inferiority: MenABCWY vs. rMenB+OMV NZ

As a sensitivity analysis, a parametric model will be run. A generalized linear model with factors for vaccine group and randomization factors (i.e. region (US/ex-US), age category (10-17 YoA/18-25 YoA), previous MenACWY vaccination (y/n)) will be ran, with the Binary distribution and link function is identity, and outcome is bactericidal activity measured by enc-hSBA at 1:4 dilution. If the lower limit of the two-sided 97.5% CI for the difference in percentage of samples with bactericidal activity measured by enc-hSBA at 1:4 dilution between the 2 groups (ABCWY (pooled) lots –MenB) coming from the model is above -5%, also the sensitivity analysis has demonstrated non-inferiority. If the co-primary effectiveness objectives for rMenB+OMV NZ are met (Sections 5.3.1.1 through 5.3.1.6), then the above will be evaluated at 95% CI.

In addition to the comparison of MenABCWY vs the selected MenB schedule per Section 5.3.1.10, MenABCWY will be compared to the other MenB schedule/schedules, whichever is applicable in the same way as described in Section 5.3.1.10. If MenB 0,2 schedule is selected as comparator, in addition MenABCWY will be compared to Menb 0,6 and MenB 0,2,6 schedule. If MenB 0,6 schedule is selected as comparator, in addition MenABCWY will be compared to MenB 0,2,6 schedule. No success criterion is defined for these group comparisons.

**5.3.2.11. Effectiveness (Responder-based): MenABCWY**

Not applicable

**5.4. Secondary effectiveness and immunogenicity****5.4.1. Analysis of secondary effectiveness and immunogenicity planned in the protocol****5.4.1.1. Immunological non-inferiority: MenABCWY vs. rMenB+OMV NZ**

Analysis set: PPS will be the primary analysis population.

Statistical method: The percentages of subjects with 4-fold rise\*\* in hSBA titres against N. meningitidis serogroup B indicator strains (M14459, 96217, M07-0241084\* and NZ98/254 for fHbp, Nada, NHBA and PorA P1.4 antigens, respectively) at 1 month after the last vaccination for the ABCWY group (pooled lots) (Day 211, Month 7) and 1 month after the 3-dose vaccination series (Day 211, Month 7) in MenB\_0\_2\_6 group or 2-dose vaccination series (Day 211, Month 7) in MenB\_0\_6 group or 2-dose vaccination series (Day 91, Month 3) in MenB\_0\_2\_6 group and the corresponding exact 2-sided 95% CIs based on Clopper-Pearson method will be calculated [Clopper, 1934]. The 95% CIs for the difference in percentages between ABCWY group (pooled lots) and MenB\_0\_2\_6 group and MenB\_0\_6 group will be constructed using the method of Miettinen and Nurminen [Miettinen, 1985].

Non-inferiority criterion: Non-inferiority of MenABCWY vaccine for the proportion of subjects with 4-fold rise will be demonstrated if the lower limit of the 2-sided 95% CI for the difference in percentage of subjects with 4-fold rise between the 2 groups (ABCWY group (pooled lots) –selected MenB group) is above -10%.

\* The NHBA indicator strain may be subject to change during the study, before clinical testing starts. In this case, this change will be documented either in a protocol amendment or in the clinical report.

\*\* For the MenB evaluation, the 4-fold rise per each indicator strain is defined as:

- a post-vaccination‡ hSBA titre  $\geq 4$  times the LOD for subjects with a pre-vaccination hSBA titre  $< \text{LOD}$
- a post-vaccination‡ hSBA titre  $\geq 4$  times the LLOQ for subjects with a pre-vaccination hSBA titre  $\geq \text{LOD}$  and  $< \text{LLOQ}$ , and
- a post-vaccination‡ hSBA titre  $\geq 4$  times the pre-vaccination hSBA titre for subjects with a pre-vaccination hSBA titre  $\geq \text{LLOQ}$

‡ = post-2nd vaccination for 0,6 and 0,2 schedule and post-3rd vaccination for 0,2,6 schedule).

Table 6 reads the LOD and LLOQ of hSBA titres against *N. meningitidis* serogroup B indicator strains used in the definition of 4-fold rise provided by the laboratory.

**Table 6 LOD and LLOQ of hSBA titres against *N. meningitidis* serogroup B indicator strains**

Strain	LOD	LLOQ
NZ98-254	CC1	
96217		
M14459		
M13520		

**5.4.1.2. Effectiveness by each of the endemic US *N. meningitidis* serogroup B strains**

Analysis set: FAS will be the primary analysis population. The ABCWY (pooled lots) group and the MenB group comparator that will be selected (ref: the footnote of Figure 2) will be used for the purpose of this analysis.

Statistical method: The VE per strain will be calculated as described in Section 5.3.1.1, using a generalised linear model with vaccine group, and randomization factors (i.e. region (US/ex-US), age category (10-17 YoA/18-25 YoA), previous MenACWY vaccination (y/n)) as independent variables, and alpha=0.05 leading to 95% CI. In case for a strain 100% response will be observed in both vaccine groups, VE against these strain will be assessed by calculating 95% CI for relative risk from raw proportions, and VE=1-RR.

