**CONFIDENTIAL**

205416 [MENB REC 2ND GEN-038 (V72\_72)]

Statistical Analysis Plan Amendment 4

Objectives	Endpoints

subjects achieving a 4-fold rise** in hSBA titres against N. meningitidis serogroup B indicator strains is above -10%.
	

To assess the effectiveness of the rMenB+OMV NZ and MenABCWY vaccines against each of the randomly selected endemic US N. meningitidis serogroup B invasive disease strains as measured by bactericidal activity using enc-hSBA at 1 month after the 3-dose (0,2,6-months in MenB_0_2_6 group) and 2-dose (0,6-months in MenB_0_6 group, 0,2-months in MenB_0_2_6 group and 0,6-months in the ABCWY (pooled) group) vaccination series when compared to 1 month after the MenACWY vaccination.
	
The percentages of samples without bactericidal serum activity using enc-hSBA against each of the endemic US N. meningitidis serogroup B strains at 1 month after the:
 
 
3-dose vaccination series (Day 211, Month 7 in MenB_0_2_6 group)
 
2-dose vaccination series (Day 211, Month 7 in MenB_0_6 group)
 
2-dose vaccination series (Day 91, Month 3 in MenB_0_2_6 group)
 
last vaccination for the ABCWY group (pooled lots) (Day 211, Month 7), and
 
MenACWY vaccination (Day 31, Month 1 in ACWY group).
 

To describe the distribution of subjects by percentages of serogroup B invasive disease strains killed using enc-hSBA at 1 month after the 3-dose (0,2,6-months in MenB_0_2_6 group) and 2-dose (0,6-months in MenB_0_6 group, 0,2-months in MenB_0_2_6 group and 0,6-months in the ABCWY (pooled) group) vaccination series of rMenB+OMV NZ and MenABCWY vaccines.
	
The percentages of serogroup B invasive disease strains killed using enc-hSBA in each subject at 1 month after the:
 
 
3-dose vaccination series (Day 211, Month 7 in MenB_0_2_6 group)
 
2-dose vaccination series (Day 211, Month 7 in MenB_0_6 group)
 
2-dose vaccination series (Day 91, Month 3 in MenB_0_2_6 group), and
 
last vaccination for the ABCWY group (pooled lots) (Day 211, Month 7)
 

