##### 5.4.2.2. Effectiveness by each of the endemic US *N. meningitidis* serogroup B strains

The SAS code to analyse the Vaccine effectiveness (Test-based): rMenB+OMV NZ - 3 doses (0,2,6-months schedule) by strain is specified below. Treatment, and randomization factors (i.e. region (US/ex-US), age category (10-17 YoA/18-25 YoA), previous MenACWY vaccination (y/n)) will be modelled as fixed effect. To account for a possible over-dispersion, the DSSCALE option in the model statement will be evaluated first. The DSSCALE will be kept in the model only if the F-statistics for the DSSCALE parameter is significant ( $p < 0.05$ ). The following SAS code will be used for the VE calculation:

```

ods trace on;
ods output GEEEmpPEst = genmod_stats
CONVERGENCESTATUS = converge ;

PROC GENMOD data=dataset descending;
class trtgrp region agecat previousACWY;
by strain ;
model outcome = trtgrp region agecat previousACWY / dist= bin link= log
DSCALE alpha=0.05;
estimate 'MenB026-ACWY' trtgrp 1 0 0 0 0 -1/ alpha= 0.05 exp;

/*trtgrp R is MenB0,2,6 and trtgrp W is ACWY*/

run;

ods output close;

data genmod_stats;
set genmod_stats;
by strain ;
where parm = 'trtgrp' and levell = '1';
rr = exp(estimate);
ub = exp(uppercl);
ve = (1 - rr)*100 ;
ve_ll = (1 - ub) * 100 ;
if ve_ll > 65 then success = 1 ;
else success = 0 ;
run;

```

where outcome represents the Bernoulli distributed outcome without bactericidal activity at a 1:4 dilution (i.e. response is 1 if titre < 4, and 0 if titre  $\geq$  4), one month after the 3rd vaccination in MenB0,2,6 and one month after the MenACWY vaccination for the ACWY arm, trtgrp indicates the vaccine groups, strain is the serogroup B strain variable, region is either US or ex-US, agecat is the age at enrolment (10-17 YoA or 18-25 YoA), and previousACWY is previous ACWY vaccination (y/n) at enrolment.

rr is the relative risk (RR), which is obtained from the estimated parameters from PROC GENMOD. Vaccine effectiveness (VE) is then derived as (1-rr)x100%.

ub represents the upper bound of the 95% CI of the relative risk. ve\_ll is the lower bound of the 95% CI for VE, if the value is greater than 65%, then the Vaccine effectiveness (Test-based): rMenB+OMV NZ - 3 doses (0,2,6-months schedule) objective is successful.

In summary in case of convergence issue the following hierarchical decision tree will be applied

- Binary model including region, agecat, and previousACWY
- Binary model, excluding region, agecat, and previousACWY

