## **6. ANALYSIS INTERPRETATION**

Multiple objectives and endpoints require type I error control. Full alpha (0.05) is split equally ( $\alpha=0.025$ ) between rMenB+OMV NZ objectives and MenABCWY objectives. Furthermore, within rMenB+OMV NZ, as well as within MenABCWY, objectives are tested hierarchically. If the first null hypothesis is rejected, then the testing will continue with the second hypothesis at same alpha. Same for 3rd, 4th, and so forth. Whenever a null hypothesis is not rejected, then the testing will stop.

As the comparator for MenABCWY non inferiority objective for the B component will be the selected schedule of rMenB+OMV NZ as determined in this study, the objectives of rMenB+OMV NZ will be analysed first. Additionally, if all null hypotheses related to rMenB+OMV NZ objectives will be rejected, the alpha ( $\alpha=0.025$ ) will be propagated to the MenABCWY part, and hypotheses related to MenABCWY objectives will be tested at full alpha ( $\alpha=0.05$ ). See Figure 2 for an explanation of the hierarchical testing (top to bottom, the order indicated by the arrows).

**Figure 2** Hierarchical testing of hypothesis

\* Alpha split equally between rMenB+OMV NZ and MenABCWY vaccine objectives.

If all rMenB+OMV NZ objectives achieved, MenABCWY vaccine objectives will be tested at full alpha.

\*\* If all objectives of rMenB+OMV NZ are met, the comparator will be the 0,2-months schedule. If the 0,2-months objective is not met, and the 0,6-months is met, then the 0,6-months schedule will be the comparator. If the 0,6-months is also not met, then the 0,2,6-months schedule will be the comparator.

Refer to Glossary of terms for definitions of test-based and responder-based vaccine effectiveness.

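### SAP Amendment 4: Table 1 sets per-strain VE for all three rMenB+OMV NZ schedules, but Section 5.4.1.2 analyses only the one selected as comparator, leaving one or two schedules without a stated estimate

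*SAP*

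**What the plan says.** All references are to SAP Amendment 4 unless stated.

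- **Table 1, secondary objectives.** The per-strain objective covers the three-dose 0,2,6 schedule and the "2-dose (0,6-months in MenB_0_6 group, 0,2-months in MenB_0_2_6 group and 0,6-months in the ABCWY (pooled) group) vaccination series when compared to" the ACWY group. The endpoint column repeats these four series and adds the control: "MenACWY vaccination (Day 31, Month 1 in ACWY group".
- **Section 5.4.1.2.** The analysis-set paragraph names the groups to be used for this analysis, with a reference to the Figure 2 footnote: "The ABCWY (pooled lots) group and the MenB group comparator that will be selected". The method is the log-link model of Section 5.3.1.1, fitted per strain with a 95% CI.
- **Section 6, Figure 2 footnote.** The selection rule starts with "If all objectives of rMenB+OMV NZ are met, the comparator will be the 0,2-months schedule", steps down to 0,6, and ends with "If the 0,6-months is also not met, then the 0,2,6-months schedule will be the comparator".
- **Section 5.4.2.2.** The by-strain code contains one contrast: "estimate 'MenB026-ACWY' trtgrp 1 0 0 0 0 -1/ alpha= 0.05 exp".
- **Section 5.4.1.3** (distribution of percentage of strains killed). It repeats the restricting sentence, but its method paragraph lists all three rMenB schedules and pooled MenABCWY.

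**The concern.** The objective and its analysis section do not cover the same schedules. Table 1 asks for a strain-by-strain picture of three rMenB schedules, Section 5.4.1.2 takes data from one, and the code names one that need not be the same. If every rMenB objective is met, the text points to 0,2, the code points to 0,6's three-dose counterpart (0,2,6), and 0,6 appears in neither.

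Two things are at stake. A programmer who follows the SAP literally would leave part of a pre-specified secondary endpoint unreported. And because the comparator is chosen from the primary results, which schedules get per-strain estimates would depend on those results. Per-strain VE is the output that shows how activity varies over the panel, so the gap would be visible in the report.

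**Working it through.** The SAP gives no count or power figure for this analysis, so there is none to reproduce. The check compares two sets.

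**Inputs**

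- rMenB schedules in the objective (Table 1): {0,2,6; 0,6; 0,2}, which is 3.
- Strains in the panel (Section 3.1 and Glossary): 110.
- Schedules selected by the Figure 2 footnote (Section 6): exactly one in every branch.
- Contrast written in Section 5.4.2.2: 0,2,6 versus ACWY, with no reference to the selection.

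**Formula.** Schedules without an estimate = objective set minus covered set. Estimates lost = 110 × number of such schedules. The objective implies 110 × 3 = 330 rMenB estimates. Pooled MenABCWY is kept in Section 5.4.1.2 and is not counted.

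| Selected comparator | Not covered, Section 5.4.1.2 alone | Lost | Not covered if the 0,2,6 code is also run | Lost |
|---|---|---|---|---|
| 0,2 (all rMenB objectives met) | 0,6 and 0,2,6 | 220 | 0,6 | 110 |
| 0,6 | 0,2 and 0,2,6 | 220 | 0,2 | 110 |
| 0,2,6 | 0,2 and 0,6 | 220 | 0,2 and 0,6 | 220 |

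The loss is therefore one to two schedules, or 110 to 220 of 330 estimates.

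**Does another section close the gap?** Section 5.3.2.10 extends an analysis to the unselected schedules, but only for the non-inferiority comparison of MenABCWY with rMenB+OMV NZ. No matching sentence exists for per-strain VE. Section 8 declares no change from planned analyses, so the narrowing is not announced there.

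**Does a looser reading close it?** The phrase in Section 5.4.1.2 could mean the randomised group instead of the schedule. MenB_0_2_6 supplies both the 0,2 and the 0,2,6 data, so selecting either would cover two schedules. MenB_0_6 would still be left out. If 0,6 were selected, at least 0,2 would be left out. At least one schedule is missing on every reading.

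**The case against.** The case against has real weight, and several parts of it stand.

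- **Version.** The text is Amendment 4. Amendment 5 exists, but its Section 5.4.1.2 is not in the part available here. This stands: the conflict is shown for Amendments 2, 3 and 4 and is unverified for Amendment 5.
- **The code still yields 0,2,6.** A reader might infer from Section 5.4.1.2 that full success leaves both 0,6 and 0,2,6 without per-strain VE. The SAP as a whole does not support that, because Section 5.4.2.2 writes 0,2,6 versus ACWY whichever schedule is selected. With full success, only 0,6 has no stated estimate.
- **The code may be a template.** Its contrast has six coefficients, one per randomised group, and the primary analysis supplies 0,6 and pooled MenABCWY contrasts (Sections 5.3.2.3 and 5.3.2.9) and the 0,2 data swap (Section 5.3.2.5). This suggests that the authors may have intended every schedule. It does not override an analysis-set sentence that says otherwise.
- **The ACWY arm.** A reader might infer that the reference arm is missing because Section 5.4.1.2 does not list it. It is supplied by the reference to Section 5.3.1.1, by Table 1 and by the code.
- **Section 5.4.1.3.** A reader might infer that the distribution of strains killed is also lost for two schedules. Its own method paragraph lists all of them, so this is an internal inconsistency and no loss is shown.
- **Rationale.** Section 3.1 speaks of confirming that the vaccine protects against diverse strains. It does not ask for that schedule by schedule, so the case rests on Table 1.
- **Consequence.** Table 1 attaches no success criterion to this objective, and all three schedules keep their primary test-based and responder-based analyses. The 65% success flag in the by-strain code does not turn it into a confirmatory test.

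**Conclusion.** The concern holds in limited form. In Amendment 4, Table 1 and Section 5.4.1.2 disagree on which rMenB schedules receive per-strain VE, and the code in Section 5.4.2.2 matches neither unless 0,2,6 happens to be selected. The size is two schedules (220 of 330 estimates) under Section 5.4.1.2 alone. If the 0,2,6 code is run regardless of selection, it is one (110) when 0,2 or 0,6 is selected and two (220) when 0,2,6 is selected.

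This assumes that the Figure 2 footnote selects a schedule, as its wording says, and that the SAP is followed literally. It concerns a descriptive secondary endpoint, and no primary conclusion changes. It should be corrected because, as written, the primary results decide what part of a pre-specified endpoint is reported.

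**What to change.** 1. In Sections 5.4.1.2 and 5.4.1.3, delete the sentence limiting the analysis to the selected comparator. Check Amendment 5 and make the same change there if the sentence was carried forward.
2. State in both sections that rMenB+OMV NZ 0,2,6, 0,6 and 0,2 and pooled MenABCWY are each analysed. For per-strain VE, name ACWY at Day 31 as the reference.
3. In Section 5.4.2.2, give four contrasts versus ACWY: 0,2,6, 0,6, 0,2 (with Day 91 data from MenB_0_2_6) and pooled MenABCWY.

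If the narrowing was intended, Table 1 would have to be cut to match and the change declared in Section 8. That is the weaker choice, because reporting would still depend on the primary results.

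The cost is SAP wording, three further contrasts and additional output tables. No new assays should be needed, since the primary test-based objectives already call for strain-level enc-hSBA results for all three schedules and for ACWY. This assumes that laboratory testing of a schedule is not withheld when the testing hierarchy stops early.

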**5.4.1.3. Distribution of percentages of serogroup B invasive disease strains killed**

Analysis set: FAS will be the primary analysis population. The ABCWY (pooled lots) group and the MenB group comparator that will be selected (ref: the footnote of Figure 2) will be used for the purpose of this analysis.

Statistical method: Summary statistics of the percentage of serogroup B invasive disease strains killed within a subject using enc-hSBA at 1 month after the 3-dose (0,2,6-months in MenB\_0\_2\_6 group) and 2-dose (0,6-months in MenB\_0\_6 group, 0,2-months in MenB\_0\_2\_6 group and 0,6-months in the ABCWY (pooled) group) vaccination series of rMenB+OMV NZ and MenACWY vaccines.

Summary statistics and 95% CI for the mean percentage will be presented, as well as a Figure of the cumulative distribution function.

**5.4.1.4. Immune response of MenABCWY, rMenB+OMV NZ and MenACWY**

Analysis set: The analysis will be based on the FAS.

Statistical method: The hSBA titres at each time point for all groups (ABCWY group (pooled lots), MenB\_0\_2\_6 and MenB\_0\_6 groups) will be logarithmically transformed (base10) to fulfil the normal distribution assumption. For each *N. meningitidis* serogroup A, C, W and Y and each B indicator strain (M14459, 96217, M07-0241084\* and NZ98/254 for fHbp, NadA, NHBA and PorA P1.4 antigens, respectively), the GMTs and GMRs (post-vaccination/baseline) will be obtained from an Analysis of Variance (ANOVA) with factors for vaccine group, region (US/ex-US), age category (10-17 YoA/18-25 YoA), and previous MenACWY vaccination (y/n), and then exponentiating the log-transformed means and their 95% CIs. The ratio of GMTs and GMRs between two groups and the corresponding CI will be estimated additionally.

The total IgG (as measured by ECL) against serogroups A, C, W and Y at baseline (Day 1, Month 0) and

- at 1 month after the first (Day 31, Month 1) and the last vaccination (Day 211, Month 7) for the ABCWY group (pooled lots), and
- at 1 month after the MenACWY vaccination in the ACWY group (Day 31, Month 1),

will be analyzed in a comparable way as described above for hSBA titres. Since total IgG is measured as concentration instead of titer, the resulting geometric mean of the concentrations is abbreviated as GMC.

**Table 7 LLOQ of total IgG (as measured by ECL) MenACWY indicator strains**

Strain	LLOQ
Men A	CCI
Men C	
Men W	
Men Y	

For each *N. meningitidis* A, C, W and Y and for each (individual response) and all (composite response) serogroup B indicator strain (M14459, M07-0241084\*, 96217 and NZ98/254) the percentages of subjects with hSBA titres  $\geq$ LLOQ and of subjects with 4-fold rise and the corresponding exact 2-sided 95% CIs based on Clopper-Pearson method will be calculated for each study group at each timepoint not previously analyzed. Ninety-five percent (95%) CIs for the difference in percentages between ABCWY (pooled lots) on the one hand and MenB\_0\_2\_6, MenB\_0\_6, and ACWY groups, respectively, on the other hand, will be constructed using the method of Miettinen and Nurminen [Miettinen, 1985].

\* The NHBA indicator strain may be subject to change during the study, before clinical testing starts. In this case, this change will be documented either in a protocol amendment or in the clinical report.

#### 5.4.2. Additional considerations

##### 5.4.2.1. Immunological non-inferiority: MenABCWY vs. rMenB+OMV NZ

As a sensitivity analysis, a parametric model will be run. A generalized linear model with factors for vaccine group and randomization factors (i.e. region (US/ex-US), age category (10-17 YoA/18-25 YoA), previous MenACWY vaccination (y/n)) will be ran, with the Binary distribution and link function is identity, and outcome is 4-fold rise. If the lower limit of the two-sided 95% CI for the difference in percentage of subjects with 4-fold rise between the 2 groups (ABCWY (pooled) lots –MenB) coming from the model is above -10%, also the sensitivity analysis has demonstrated non-inferiority.

##### 5.4.2.2. Effectiveness by each of the endemic US *N. meningitidis* serogroup B strains

The SAS code to analyse the Vaccine effectiveness (Test-based): rMenB+OMV NZ - 3 doses (0,2,6-months schedule) by strain is specified below. Treatment, and randomization factors (i.e. region (US/ex-US), age category (10-17 YoA/18-25 YoA), previous MenACWY vaccination (y/n)) will be modelled as fixed effect. To account for a possible over-dispersion, the DSSCALE option in the model statement will be evaluated first. The DSSCALE will be kept in the model only if the F-statistics for the DSSCALE parameter is significant ( $p < 0.05$ ). The following SAS code will be used for the VE calculation:

```

ods trace on;
ods output GEEEmpPEst = genmod_stats
CONVERGENCESTATUS = converge ;

PROC GENMOD data=dataset descending;
class trtgrp region agecat previousACWY;
by strain ;
model outcome = trtgrp region agecat previousACWY / dist= bin link= log
DSCALE alpha=0.05;
estimate 'MenB026-ACWY' trtgrp 1 0 0 0 0 -1/ alpha= 0.05 exp;

/*trtgrp R is MenB0,2,6 and trtgrp W is ACWY*/

run;

ods output close;

data genmod_stats;
set genmod_stats;
by strain ;
where parm = 'trtgrp' and levell = '1';
rr = exp(estimate);
ub = exp(uppercl);
ve = (1 - rr)*100 ;
ve_ll = (1 - ub) * 100 ;
if ve_ll > 65 then success = 1 ;
else success = 0 ;
run;

```

where outcome represents the Bernoulli distributed outcome without bactericidal activity at a 1:4 dilution (i.e. response is 1 if titre < 4, and 0 if titre  $\geq$  4), one month after the 3rd vaccination in MenB0,2,6 and one month after the MenACWY vaccination for the ACWY arm, trtgrp indicates the vaccine groups, strain is the serogroup B strain variable, region is either US or ex-US, agecat is the age at enrolment (10-17 YoA or 18-25 YoA), and previousACWY is previous ACWY vaccination (y/n) at enrolment.

rr is the relative risk (RR), which is obtained from the estimated parameters from PROC GENMOD. Vaccine effectiveness (VE) is then derived as (1-rr)x100%.

ub represents the upper bound of the 95% CI of the relative risk. ve\_ll is the lower bound of the 95% CI for VE, if the value is greater than 65%, then the Vaccine effectiveness (Test-based): rMenB+OMV NZ - 3 doses (0,2,6-months schedule) objective is successful.

In summary in case of convergence issue the following hierarchical decision tree will be applied

- Binary model including region, agecat, and previousACWY
- Binary model, excluding region, agecat, and previousACWY
- Cochran-Mantel-Haenszel (CMH) method (if strain has 100% killed or 0% killed for ANY treatment)

- VE set to 0% (if strain has 100% killed for both treatment)

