#### **5.3.1.1. Vaccine effectiveness (Test-based): rMenB+OMV NZ - 3 doses (0,2,6-months schedule)**

Analysis set: Per-protocol set (PPS) will be the primary analysis population

Statistical method: The VE is defined as  $1 - RR = (1 - \text{percentage of samples without bactericidal serum activity at 1:4 dilution in MenB group} / \text{percentage of samples without bactericidal serum activity at 1:4 dilution in the ACWY group}) \times 100\%$  and it will be analyzed using a generalised linear model with vaccine group, strain, and randomization factors (i.e. region (US/ex-US), age category (10-17 YoA/18-25 YoA), previous MenACWY vaccination (y/n)) as independent variables. Furthermore, a repeated statement will be used to estimate the variance of the RR including correlation within subject's responses to different strains. If the statistical model does not converge due to (one of) the factor(s), a model without this/these factor(s) will be fitted instead. The response variable of the model will be the Bernoulli distributed outcome without bactericidal activity at a 1:4 dilution (i.e. response is 1 if titre  $< 4$ , and 0 if titre  $\geq 4$ ), at 1 month after the last vaccination (Month 7) in the MenB group and at Month 1 for the ACWY group. Each subject will contribute with approximately 35 measures to this analysis, each of the measures corresponding to the response variable to one of the 35 strains randomly assigned to be tested with the samples available for that specific subject.

In order to obtain the VE measure which is a measure based on the relative risk (RR), a generalised linear model will be used with the Binary distribution and link function log in order to compute the log RR and the corresponding 97.5% CI. The obtained values will be exponentiated to obtain the RR and the corresponding 97.5% CI. The VE will be computed as  $100\% \times (1 - RR)$ . Effectiveness of rMenB+OMV NZ (0,2,6-months schedule) will be demonstrated if the lower limit of the two-sided 97.5% CI for VE between MenB and the ACWY group is above 65%.

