#### 5.3.2.1. Vaccine effectiveness (Test-based): rMenB+OMV NZ - 3 doses (0,2,6-months schedule)

The SAS code to analyse the Vaccine effectiveness (Test-based): rMenB+OMV NZ - 3 doses (0,2,6-months schedule) objective is specified below. Treatment, region, age category, previous ACWY vaccination, and strains will be modelled as fixed effect. To account for a possible over-dispersion, the DSCALE option in the model statement will be evaluated first. The DSCALE will be kept in the model only if the F-statistics for the DSCALE parameter is significant ( $p<0.05$ ). The following SAS code will be used for the VE calculation:

```

ods trace on;
ods output GEEmpPEst = genmod_stats
CONVERGENCESTATUS = converge ;

PROC GENMOD data=dataset descending;
class trtgrp strain region agecat previousACWY subject_id ;
model outcome = trtgrp strain region agecat previousACWY / dist= bin
link= log DSCALE;
repeated subject = subject_id / type= CS withinsubject= strain;
estimate 'MenB026-ACWY' trtgrp 1 0 0 0 0 -1/ alpha=0.025 exp;

/*trtgrp R is MenB0,2,6 and trtgrp W is ACWY*/

run;

ods output close;

data genmod_stats;
set genmod_stats;
where parm = 'trtgrp' and level1 = '1';
rr = exp(estimate);
ub = exp(uppercl);
ve = (1 - rr)*100 ;
ve_ll = (1 - ub) * 100 ;
if ve_ll > 65 then success = 1 ;
else success = 0 ;
run;

```

where outcome represents the Bernoulli distributed outcome without bactericidal activity at a 1:4 dilution (i.e. response is 1 if titre  $< 4$ , and 0 if titre  $\geq 4$ ), one month after the 3rd vaccination in MenB 0,2,6 and one month after the MenACWY vaccination for the ACWY arm, trtgrp indicates the vaccine groups, strain is the serogroup B strain variable, region is either US or ex-US, agecat is the age at enrolment (10-17 YoA or 18-25 YoA), and previousACWY is previous ACWY vaccination (y/n) at enrolment.

rr is the relative risk (RR), which is obtained from the estimated parameters from PROC GENMOD. Vaccine effectiveness (VE) is then derived as (1-rr)x100%.

ub represents the upper bound of the 97.5% CI of the relative risk. ve\_ll is the lower bound of the 97.5% CI for VE, if the value is greater than 65%, then the Vaccine effectiveness (Test-based): rMenB+OMV NZ - 3 doses (0,2,6-months schedule) objective is successful.

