#### 10.3. Glossary of terms

End of Study (EoS) (Synonym of End of Trial)	For studies with collection of human biological samples and/or imaging data, the EoS is defined as Last subject last visit (T10). or Last testing results released of samples collected at Visit 6*  * In this case EoS must be achieved no later than 8 months after LSLV.
Primary completion date:	The date that the final subject was examined or received an intervention for the purpose of final collection of data for all primary outcomes, whether the clinical trial was concluded according to the pre-specified protocol or was terminated.
Responder-based vaccine effectiveness:	The enc-hSBA methodology involves testing the serum samples from each individual subject against a subset of around 35 strains randomly chosen from the overall panel of 110 meningococcus B US strains. Responder-based vaccine effectiveness is assessed based on the percentage of subjects considered responders, i.e., subjects whose serum kills the majority ( $\geq 70\%$ in this study) of the tested strains following vaccination.
Test-based vaccine effectiveness:	The enc-hSBA methodology involves testing the serum samples from each individual subject against a subset of around 35 strains randomly chosen from the overall panel of 110 meningococcus B US strains. Test-based vaccine effectiveness is assessed based on the overall percent of individual positive tests following vaccination and represents the reduction in risk compared to the placebo.

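### In the by-strain VE model, DSCALE has no valid use with one 0/1 result per subject, its retention rule cannot be carried out as written, and if kept it mis-scales the 95% CIs

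*SAP*

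**What the plan says.** Section 5.4.2.2 (Amendment 4) gives the by-strain code. The outcome is binary: "where outcome represents the Bernoulli distributed outcome without bactericidal activity at a 1:4 dilution", coded 1 if the titre is below 4 and 0 otherwise. The model is run BY strain as "model outcome = trtgrp region agecat previousACWY / dist= bin link= log", and the statement continues with "DSCALE alpha=0.05". There is no REPEATED statement, so the standard errors are model-based.

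The stated reason for the option is "To account for a possible over-dispersion, the DSSCALE option in the model statement will be evaluated first" (the prose spells it with a double S). The retention rule is "The DSSCALE will be kept in the model only if the F-statistics for the DSSCALE parameter is significant", at p<0.05. The test is not defined, and no direction is given. The section then introduces the printed code as the code that will be used, and that code contains DSCALE.

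On the data structure, section 5.3.1.1 says "Each subject will contribute with approximately 35 measures to this analysis", and the glossary (10.3) describes a "subset of around 35 strains randomly chosen from the overall panel of 110 meningococcus B US strains". The roughly 35 results of one subject are therefore against different strains.

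Section 5.3.2.1, the overall VE model, has the parallel rule "The DSCALE will be kept in the model only if the F-statistics for the DSCALE parameter is significant", but there the code has a REPEATED statement and takes its limits from the GEE empirical estimates.

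**The concern.** DSCALE estimates a dispersion as deviance divided by degrees of freedom and multiplies every model-based standard error by its square root. That makes sense for grouped counts, where the deviance measures lack of fit. With single 0/1 observations it does not. A Bernoulli variance is fixed by its mean, so there is no extra variation to detect, and the deviance is simply a function of the fitted probabilities. The factor falls below 1 when few samples are unkilled and rises above 1 when about half are.

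At stake are the 95% CIs for up to 110 strains in each comparison. If the option is kept, the intervals come out too narrow for the strains the vaccine covers best and too wide for those with mid-range rates. The by-strain code also sets a success flag when the lower VE limit exceeds 65%, so a mis-scaled limit can change the flag.

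**Working it through.** **Inputs from the SAP.** Section 3.3 gives 912, 548 and 183 randomised per MenB group, ABCWY lot and ACWY group, with 25% drop-out. 912 × 0.75 = 684, 548 × 0.75 = 411 and 183 × 0.75 = 137.25, which reproduces the stated 684, 411 and 137. With 35 of 110 strains per subject, the numbers per strain are:
- MenB group: 684 × 35/110 = 217.6
- ABCWY lot: 411 × 35/110 = 130.8
- ACWY: 137 × 35/110 = 43.6
- all vaccinees: 2 × 217.6 + 3 × 130.8 = 827.6

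**Assumptions, not in the SAP.** The unkilled proportions are p1 in vaccinees (common to all vaccine groups) and p0 in ACWY. The deviance is taken over single observations, because the code has no aggregation option.

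**Formula.** The expected deviance per 0/1 observation is d(p) = −2[p ln p + (1−p) ln(1−p)]: d(0.02) = 0.196, d(0.05) = 0.397, d(0.10) = 0.650, d(0.20) = 1.001, d(0.50) = 1.386. The DSCALE factor on the standard error is approximately

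sqrt{[n1·d(p1) + n0·d(p0)] / (n1 + n0)}.

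It contains no term for dispersion. Its maximum at any rate is sqrt(1.386) = 1.18.

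**One value in full.** For p1 = 2% and p0 = 75%, d(0.75) = 1.125.
- All six groups: sqrt[(827.6 × 0.196 + 43.6 × 1.125)/871.2] = 0.49
- One MenB group plus ACWY: sqrt[(217.6 × 0.196 + 43.6 × 1.125)/261.2] = 0.59

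**Range over p0 from 0.50 to 0.98 and both fits:**

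| p1 unkilled | CI width (log RR) relative to correct |
|---|---|
| 2% | 0.44–0.63 |
| 5% | 0.60–0.75 |
| 10% | 0.76–0.88 |
| 20% | 0.93–1.03 |
| 30% | 1.03–1.12 |
| near 50% | up to 1.18 |

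**Coverage.** Simulation (4000 replicates, p0 = 90%, two-group and six-group fits) of the nominal 95% CI:

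| p1 | with DSCALE | without |
|---|---|---|
| 2% | 65–67% | 96–97% |
| 5% | 80% | 96% |
| 10% | 89% | 95% |
| 20% | 94–95% | 95–96% |
| 40% | 97–98% | 95–96% |

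**Examples with assumed counts.**
- 11/218 against 40/44 unkilled: VE 94.4%, SE of log RR 0.298. The CI is 90.1 to 96.9 with scale 1, and 91.8 to 96.2 with the two-group factor of 0.66.
- 5/218 against 8/44 unkilled: VE 87.4%. The lower limit is 63.2% with scale 1, but 76.4% (two-group fit) or 78.3% (six-group fit) with DSCALE. The flag at 65% changes. This needs a strain that few control samples fail to kill.

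**The case against.** The strongest reply is that the plan makes DSCALE conditional. A reader might infer from the printed code that the by-strain CIs will be rescaled outright, to as little as half their proper width. The documents do not support that. The prose keeps the option only on a significant test. If no such test can be computed, the condition is never met and DSCALE drops out. If the rule is read as a test for over-dispersion, strains with deviance/df below 1 would also drop it, and nothing would narrow. Narrowing needs the printed code run as it stands, or a reading of significance that includes under-dispersion. This stands. What remains is that the prose and the printed code point different ways, and two programmers could report different CIs for the same strain.

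The printed code is also not a safe guide to what will be run. It requests the GEE estimates table although the by-strain model has no REPEATED statement, so it must be edited before it yields limits.

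The size is conditional too. Half width is not a bound: below about 1% unkilled the factor can reach 0.26. It also depends on which groups are fitted. The six-level contrast points to all groups, while section 5.4.1.2 names pooled ABCWY and the selected MenB comparator. Some of the most extreme strains may leave the model through the CMH fallback.

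Finally, this is a secondary objective without a success criterion in Table 1, outside the alpha hierarchy. A reader might extend the point to the overall VE result, but section 5.3.2.1 uses empirical standard errors, so DSCALE there does no harm.

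**Conclusion.** The point holds in a conditional form. With one 0/1 result per subject in each by-strain fit, over-dispersion cannot be identified, and no reading of 5.4.2.2 gives DSCALE a valid use. The retention rule cannot be carried out as written, because the scale is a plug-in value for which the SAP defines neither test nor direction.

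If DSCALE is kept, the CIs are mis-scaled in both directions by the amounts tabulated above: too narrow for well-covered strains, too wide for those near 50% unkilled. If it is kept only for apparent over-dispersion, the remaining effect is over-widening of at most 18%. These figures rest on assumed unkilled rates, the planned evaluable numbers and a deviance taken over single observations. No primary conclusion is touched.

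The text is from Amendment 4. Amendment 5 is the latest version, and its section 5.4.2.2 lies outside the part available, so whether the option persists there is unverified.

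**What to change.** In section 5.4.2.2, delete DSCALE from the MODEL statement together with the two sentences on over-dispersion and the F-test rule, and state that the scale is fixed at 1. Check the same section of Amendment 5 and make the change there if the text is unchanged. Deleting the parallel option and rule from the overall VE code (5.3.2.1 and the sections that reuse it) is tidying only.

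The cost is one option and two sentences. Compared with a run that kept DSCALE, CIs for well-covered strains become wider and those for mid-range strains slightly narrower. No sample size, endpoint or primary test changes.
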